CCHMC IRB Protocol 2011-2045 was a pilot study including 15 neonates demonstrating safety and feasibility of the NICU MRI. Photographs from the scanning process and images from the first patients are attached in Appendix F. Permission to use the photographs was obtained from the parents of the baby.

Subsequently we have scanned nearly 600 patients on the NICU MRI without adverse event under CCHMC IRB Protocol 2011-2850.

STUDY METHODS:

This is a study to use a customized MRI system installed in the CCHMC NICU to perform medically indicated MRI exams in the neonatal population.

Study population:

Neonates admitted to CCHMC for whom an MRI exam is medically indicated will be recruited into the study. All neonates in the study will be viable, as defined in subpart B of the Code of Federal Regulations. The infants will be medically stable to undergo the MRI procedure, as determined by the attending neonatologist.

Study design:

Infants who may meet study criteria will be identified by the attending neonatologist and study staff will be notified of a potential candidate for the study. As per usual clinical care, orders for the MRI will be placed in EPIC.

Inclusion criteria:

- Any infant admitted to CCHMC
- Have a medical condition for which an MRI exam is indicated, as determined by the attending neonatologist

Exclusion criteria:

- Infants too large to fit in the customized NICU MRI system comfortably (generally infants > 6 kg)
- Standard MRI exclusion criteria as set forth by the CCHMC Division of Radiology

Pre-scan:

The attending neonatologist will determine whether the MRI scan is to be done with sedation or without sedation. Whenever possible, infants will be scanned without sedation utilizing a feed and bundle technique. Occasionally, at the discretion of the

neonatologist, sedation will be necessary to obtain the imaging required for clinical diagnosis. This mirrors the process utilized on the conventional magnets in the Department of Radiology. The use of sedation and/or contrast is not part of the research.

Prior to MRI scanning, the patient's NICU care team will attempt to contact parent/LAR to communicate that a MRI has been ordered and provide information on the device, any potential risks and answer any questions the parent/LAR may have.

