Infants will be prepared for the MRI exam at the bedside by switching all monitoring devices over to MRI compatible monitors. Switching monitoring devices confers no additional risk to the patient. Hearing protection will be used for acoustic noise reduction. Infants will then be moved to the MRI control room and transferred to the patient table/transfer station by the NICU nurse and/or physician.

Standard MRI safety screening will be performed by the MRI technologist per Department of Radiology practice. Screening will be documented according to standard Department of Radiology procedure.

MRI scan:

All studies will be performed with a nurse and/or physician in the control room. The specific MR sequences used will be determined by the type of exam to be performed based on the medical indication. Some patients may get IV contrast and/or sedation if indicated by the specific MR exam protocol. The scanner will be operated by a certified MR technologist.

Sequences will be obtained using the OPTIMA electronics during each MRI exam in order to have images from a device that is FDA cleared. Additional sequences will be obtained with the HDX/GE platform. Images from the HDX/GE platform are expected to be of diagnostic quality equal to or better than those obtained from an adult-sized 1.5T MRI scanner. If the patient remains stable throughout the MRI exam, an additional 10 minutes of scanning beyond the clinically indicated sequences may be obtained for ongoing sequence development and improvement efforts.

All coils used will be FDA cleared. Those not cleared will be submitted to the IRB and approved before they are used.

Monitoring of safety and tolerability:

Adverse events will be monitored during the MRI scan by the MRI technologist and the nurse/physician in the control room. Only adverse events that take place during MRI scanning will be recorded. Adverse events will be recorded on an adverse event log form kept in the MRI control room. In the event of an adverse event, the study team will be notified and a full report of the specific event will be submitted to the IRB promptly. Nurses will collect vital signs for clinical care purposes, but there will be no vital sign collection as part of this protocol.

6

Evaluation of MRI data:

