In regards to 45 CFR 164.501, 164.508, 164.512(i), all protected health information generated as part of this study will remain confidential in accordance with CCHMC best practices. PHI, including but not limited to, date of birth, name, medical history, must be used to safely and adequately perform and document an MR exam. PHI related to this clinical MR study will not be disclosed to any other person or entity for additional research without a specific study IRB. All images and patient data are maintained securely in CCHMC's protected clinical PACS and in EPIC, both of which have electronic access controls. Specifically, CCHMC personnel must request access to these systems from their manager and CCHMC Information Services. Granted access is dependent on their institutionally assigned job description and credentials. Clinical PACS and EPIC are highly secure systems, hosted and supervised by CCHMC network security and are HIPAA compliant.

Patient identifiers will be available to the patients' care team as part of their clinical duties. It is not possible for the study team to withhold the MR images generated as part of this study from the patient's clinical staff because they rely on them for diagnostic

9

purposes and withholding these images would deny these patients potential clinical benefit. At no point will we destroy patient identifiers as they are the patient's clinical identifiers.

In many cases the parent/LAR is not on site when the physician orders an MRI and NICU staff have to reach them by phone. Transferring NICU patients to the main Radiology Department has specific risks related to difficulties with mobile monitoring, inadequate environmental controls (for a population susceptible to heat loss) and exposure to a general hospital population. All parents/LARs of prospective patients will have the NICU MRI study explained to them by their clinical care team who order the MR scan- the nature of the scan, financial costs, and possible adverse reactions, none of which differ from conventional MRI scanners. It will be made clear that participation in the study is voluntary.

NICU fellows or attendings, who are part of the study staff, will use the study information sheet provided and the verbal script below to communicate and obtain consent from parents/LARs.

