The fellow or attending taking care of patient will call the parents/LARs and introduces him/her self. The fellow or attending then verifies that they are speaking with the correct parent/LAR using information. The physician will tell the parent/LAR that their child is scheduled to have an MRI of their brain/spine/abdomen/etc. and explain why the MRI is needed. Next, they tell them that they are calling the get their permission to use our NICU MRI. The script that follows will be used after the above introduction:

"An MRI machine uses a computer and a big magnet to take pictures. The magnet in our NICU scanner is much smaller than the magnets used in the MRI machines downstairs in the Radiology department. We are one of the only NICU's in the country that have MRI capability within the NICU as opposed to the hospital-wide radiology suite. Our MRI machine uses a smaller magnet than a typical MRI machine. Individually the MRI magnet and imaging software are FDA approved, but together as one unit they are not, therefore, I need your permission to use our NICU MRI for your child's study. We use the same process for obtaining the study and are able to get the same quality images using this machine as we would if your child were to have their MRI done in radiology, but with the added benefit of not having to travel off the unit. There are no additional risks by using the NICU MRI and in general we find it safer and more seamless to obtain the images when not having to travel off the floor. The same Radiologists read these images and we are able to bill your baby's insurance. There are no additional costs beyond the costs of an MRI in the big scanner downstairs. We will collect basic information about your child and the type of scan that was performed as part of quality control for the study. There are no known risks to the MRI scan itself and the MRI does not involve radiation. If you do not wish to have your baby's MRI performed in the NICU, we will schedule your baby to move downstairs for the MRI- sometimes it takes a little longer to schedule that. Do you have any questions for me at this time? ... Do you consent to having your baby's scan being done in our custom- built NICU MRI?"

A participant information sheet will be provided to parents/LARs. This information sheet serves as a study summary.

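### The optional 10 minutes of sequence-development scanning carries no condition on sedation, and the spoken permission script does not mention it

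*Protocol*

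**What the plan says.** **The extra minutes.** Protocol, STUDY METHODS, MRI scan: provided the infant has been stable during the exam, "an additional 10 minutes of scanning beyond the clinically indicated sequences may be obtained for ongoing sequence development and improvement efforts". No other condition is set.

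**Sedation.** The same subsection states: "Some patients may get IV contrast and/or sedation if indicated by the specific MR exam protocol". The Pre-scan subsection says that infants are scanned unsedated where possible and that occasionally, at the neonatologist's discretion, "sedation will be necessary to obtain the imaging required for clinical diagnosis". It adds: "The use of sedation and/or contrast is not part of the research".

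**Permission.** Under CONSENT, NICU fellows or attendings "will use the study information sheet provided and the verbal script below to communicate and obtain consent from parents/LARs". The script is given in full. It covers the smaller magnet, the regulatory status of magnet and software as a combined unit, comparability with a scan in Radiology, costs, the collection of basic information for quality control, and the alternative of a scan in Radiology. It does not mention added scan time or sequence development.

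**Safeguards.** "All studies will be performed with a nurse and/or physician in the control room". Under CONSENT: "It will be made clear that participation in the study is voluntary".

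**The concern.** The extra minutes are, by the protocol's own description, not needed for the infant's care. Sedation is justified only by the infant's care. Where the two meet, in an infant already sedated for a clinical exam who stays stable, the protocol gives no rule. The operator can follow the text exactly and keep that infant in the scanner, and so possibly under sedation, for a research purpose.

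The second part is disclosure. Permission is unsigned and often obtained by telephone, so the script carries much of the weight. A parent who hears only the script does not learn that non-clinical imaging may be added, and is offered a choice only between the NICU scan and a move to Radiology. There is no spoken option to accept the NICU scan without the additional minutes.

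What is at stake is patient protection and the completeness of the spoken permission, not a statistical result.

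**Working it through.** No formula applies and the plan has no figure to reproduce. The check is a side-by-side reading of every section that mentions sedation, the added scanning or the permission process.

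1. **Is the added time clinical or research?** MRI scan distinguishes three things: sequences on the cleared OPTIMA electronics, additional HDX/GE sequences, and then the 10 minutes. The HDX/GE images are meant to contribute to diagnosis. The 10 minutes are described as lying beyond what is clinically indicated and as serving sequence development. They are the non-clinical part.
2. **Who qualifies?** The only gate is stability. A sedated infant can be stable, and the same subsection expects some infants to be sedated. Sedated infants therefore qualify.
3. **Does another section close this?** Pre-scan ties the use of sedation to clinical diagnosis and declares it outside the research. Read with MRI scan, that rules out giving or re-dosing sedation for the extra minutes. It does not say whether an infant already sedated may be kept in the scanner for them. No other section addresses the question.
4. **Does the script mention the minutes?** Taken item by item, no. The line that begins "We use the same process for obtaining the study" goes on to compare the exam and its image quality with a scan in Radiology. The statement about risk likewise compares scanners. Neither speaks to scan duration, so neither is shown to be false. They simply do not disclose the added time.
5. **Could another channel disclose it?** Yes. A participant information sheet accompanies the script as a study summary, but its text is not available here. For non-English-speaking families the interpreter reads the same script, so the same omission carries over. The promise of a sheet is not limited to English speakers.
6. **How many infants?** The protocol reports average yearly consents under the prior protocol of 110 (English-speaking) and 2 (non-English-speaking): 110 + 2 = 112. If that rate continues, which is an assumption, about 112 families a year would hear the script. This does not count affected infants. That count would need the sedated fraction and the frequency with which the extra minutes are used, and the protocol gives neither.

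**The case against.** The strongest reply is that the sedation part is silence and not contradiction. Sedation is already tied to clinical need, the regimen is not described, and so it cannot be shown that 10 more minutes would lengthen sedation in any infant. The minutes are optional, limited in length and conditional on stability, with clinical staff in the control room. On disclosure, the script is one of several channels. The sheet is unseen, the care team must explain the nature of the scan, and participation is to be presented as voluntary. The script also states openly that the combined unit is not FDA approved, which is the main investigational element.

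Most of this stands, and it limits the point. It does not remove it. A rule gated on stability alone admits sedated infants, and the script, which can be read in full, leaves the minutes out.

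Two stronger readings are tempting. A reader might infer that the protocol allows sedation to be given or extended for research. It does not: nothing instructs this, and giving or re-dosing sedation for the minutes would conflict with Pre-scan. A reader might also infer that parents are not told about the minutes, or are misled. The documents do not support that either, because the sheet may disclose them and the script's comparative statements concern the scanners and not the length of the exam.

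**Conclusion.** The point holds in a narrow form. The allowance for sequence-development scanning sets no condition on sedation, so a clinically sedated infant could be kept in the scanner for research sequences. The script omits both the minutes and the option to decline them while keeping the NICU scan.

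The size is 10 minutes per exam at most, taking the stated allowance as a ceiling. The number of infants concerned may be small or zero. The conclusion rests on the protocol text alone and makes no claim about the information sheet or about actual practice. No estimate or endpoint is affected. This is an inexpensive improvement, not a flaw that undermines the study.

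**What to change.** **MRI scan.** Preferred: limit the allowance to unsedated infants by inserting *is unsedated and* into its opening condition, ahead of the stability requirement. At the least, add: *No sedation will be given, repeated or prolonged for these minutes.*

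**Verbal script.** Add one sentence: *If your baby stays stable, we may take up to 10 more minutes of pictures that are not needed for your baby's care, to help improve the scanner; you can decline this and still have the scan in the NICU.* The interpreter's reading then carries it too.

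**Information sheet.** Check it, and align it if it is silent.

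**Cost.** One IRB amendment covering these edits. There will be fewer development sequences, with none from sedated infants under the preferred option. Some parents will decline, and each refusal must reach the MR technologist before the scan.

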In order to address the need for neonatal access to high-end diagnostic MRI instrumentation, engineers and scientists in the Imaging Research Center (IRC) at CCHMC have adapted a commercially available, FDA cleared, small (21.8 cm diameter bore, as compared to 60-70 cm for a conventional scanner) 1.5T MRI system, the GE OPTIMA 430s, originally designed for adult orthopedic use. The operating manual and data sheets for this MRI system are included as Appendix A. The OPTIMA measurement control electronics and operating system software have been augmented with HDX/GE electronics and software (see Appendix B: HDX/GE platform operating manual and data sheets). The HDX/GE platform is FDA cleared and is used to operate much of the GE MRI product line, including scanners used clinically at CCHMC. The original OPTIMA electronics will remain operational with the OPTIMA hardware with the option to readily switch between the two operating platforms (i.e. HDX/GE vs. OPTIMA). This integration of the HDX/GE electronics and the OPTIMA hardware allows for advanced MR imaging more relevant to whole body and brain scanning.

An extensive detailed description of the modifications that were made to the systems to accommodate whole body MR imaging of the neonate and a detailed description of the patient table developed to accommodate the smaller size of the magnet are documented in the "BACKGROUND" section of CCHMC IRB Protocol 2011-2045 ("Pilot Study: Safety of a Customized MRI System for Neonatal Imaging") (See Appendix C: Detailed description of 1) modifications made to the MR systems to accommodate whole body MRI of the neonate; 2) patient table developed to accommodate the smaller size of the magnet).

PREVIOUS WORK IN THIS AREA:

Details of prior pre-clinical animal testing are documented in the "PREVIOUS WORK IN THIS AREA" section of CCHMC IRB Protocol 2011-2045 ("Pilot Study: Safety of a Customized MRI System for Neonatal Imaging"). (See Appendix D. Previous work done in this area on prototype neonatal MRI system). Further details about the NICU MRI system's safety testing are documented in the Previous Work In This Area section of protocol 2011-2045. The patient table, coils, specific absorption rate (SAR), acoustic noise, and peripheral nerve stimulation are all discussed. (See Appendix E: MR system safety testing data).

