As is done for any medically indicated clinical MRI exam, all images acquired will be interpreted by a board certified pediatric radiologist or neuroradiologist and a standard report will be generated. This report will be included in the neonate's medical record and made available to the clinical team. The MRI data collected using the OPTIMA/HDX MRI platform will be used in conjunction with the images obtained using the FDA cleared OPTIMA MRI platform and the results of other appropriate standard diagnostic tests to inform diagnosis and/or subsequent medical management. Deidentified images may be used in publications or in support of a 510K application to the FDA.

Sample size:

The goal of this study is to make MRI available to all neonates admitted to CCHMC for whom an MRI exam is medically indicated. Thus, the maximum number of patients recruited into the study per year will reflect the maximum number of patients admitted into the NICU. A review of the historical data documenting the number of patients admitted to the CCHMC NICU over a five year period (2006 – 2010) indicated that on average, 714 (range 662-759) patients were admitted each year over that period.

DURATION:

This protocol is considered a continued access protocol and will remain open indefinitely.

POTENTIAL BENEFITS:

By eliminating the need to transfer neonates from the NICU to the main Radiology Department for an MRI exam, neonatal patients will benefit by avoiding the medical risk associated with removal from the NICU. Patients evaluated on the NICU MRI will also benefit from reduced acoustic noise, lower RF power deposition and less chance of peripheral nerve stimulation during the MR exam as compared to that associated with exams performed on the adult sized conventional MR scanner. Patients may also benefit from earlier and/or more comprehensive and accurate diagnosis and medical management.

POTENTIAL RISKS, DISCOMFORTS, AND INCONVENIENCES:

MRI exams are considered minimal risk for research purposes. The customized NICU MRI scanner will have no increase in risk beyond conventional adult MRI scanners. Although chart review is not part of this protocol, there is a risk of loss of confidentiality

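### The adverse-event log covers only the scanning interval, so the move, the transfers onto and off the custom patient table, and the return have no entry on the only study safety log described

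*Protocol*

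**What the plan says.** All places are in the Protocol.

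- Study Methods, Monitoring of safety and tolerability, sets who watches and when: "Adverse events will be monitored during the MRI scan by the MRI technologist and the nurse/physician in the control room". It then sets what is kept: "Only adverse events that take place during MRI scanning will be recorded". Entries go on a log form held in the control room. If an event occurs, "the study team will be notified and a full report of the specific event will be submitted to the IRB promptly".
- Study Methods, Pre-scan, describes what happens before scanning. Infants are "moved to the MRI control room and transferred to the patient table/transfer station by the NICU nurse and/or physician". The transfer off the table and the return to the bedside are not described.
- Background refers to a "patient table developed to accommodate the smaller size of the magnet". Previous Work in This Area lists what the system's safety testing covers: "The patient table, coils, specific absorption rate (SAR), acoustic noise, and peripheral nerve stimulation are all discussed".
- Two other possible data sources are ruled out. Monitoring of safety and tolerability adds that "there will be no vital sign collection as part of this protocol". Potential Risks, Discomforts, and Inconveniences contains the clause "Although chart review is not part of this protocol".
- The Data Safety and Monitoring Plan has the PI review adverse events and sends unanticipated problems and adverse events to the IRB under the institution's policy. It does not limit either duty to the scan.
- Recruitment and Consent both state that the NICU fellows and attendings belong to the study team.

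**The concern.** The recording window is narrower than the use of the device. The infant is lifted onto and off a table made for this small-bore system, and the Protocol itself names that table among the items whose safety was tested. An incident while the infant is being loaded or unloaded is therefore an incident in using the customised system, yet it falls outside the interval in which events are watched for and written down.

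What is at stake is the meaning of the log. The Protocol is a continued-access protocol with no planned end, so the log will accumulate for years. If it stays empty, it shows that nothing was noted during scanning. It says nothing about table handling or the journey. The PI's review would rest on that record plus whatever individual staff chose to report.

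**Working it through.** The main check is a comparison of text. A short count of exposure follows.

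**1. Is the transfer inside the window?** Monitoring and recording are both tied to the scan. The term is not defined, and a reader could stretch it to the whole visit. Two features speak against that. The recording sentence opens with a word of restriction, and the Protocol puts the move and the transfer under Pre-scan, ahead of a separate MRI scan heading. On the Protocol's own structure, the steps compare as follows:

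| Step | Where described | Inside the log window? |
|---|---|---|
| Move to control room | Pre-scan | No |
| Transfer onto patient table | Pre-scan | No |
| Scan | MRI scan | Yes |
| Transfer off table | Not described; follows the scan | No |
| Return to bedside | Not described; follows the scan | No |

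**2. Is there another study record?** Study vital signs are excluded and chart review is excluded. A safety record is mentioned under Potential Risks, Discomforts, and Inconveniences, but only as something to be de-identified and locked away, with no content or time window of its own. Clinical staff will chart events for care, but the Protocol does not draw on those charts. The control-room log is the only safety log described.

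**3. Is there another route to the IRB?** Yes. The treating fellow or attending is study staff, and the Data Safety and Monitoring Plan reports unanticipated problems and adverse events without a scan limit. That is a reporting duty and depends on someone raising the event. It does not provide a place or a time window for recording.

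**4. How much handling is unlogged?** The Protocol states no figure for this, so there is none to reproduce. Consent gives the yearly averages under protocol 2011-2850: 110 English-speaking and 2 non-English-speaking families.

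- Consents per year: 110 + 2 = 112.
- Exams per year, assuming one exam per consent and the same rate now: 112.
- Table transfers per year, one onto and one off per exam: 2 × 112 = 224.
- Of these, transfers inside the log window: 0.

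This counts opportunities, not events. The Protocol gives no rate of events in transfer, so the number of missed entries cannot be calculated.

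**The case against.** The strongest reply is that the window is deliberate. The Protocol offers continued access to medically indicated exams, safety was the subject of the pilot study, and table testing is referred to an appendix. The rule is also clear to staff. All of this is fair, and it is why the point is a cheap improvement and not an error. It does not change what the rule leaves out.

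Four stronger readings are tempting, and the Protocol does not support them.

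- *A reader might infer that nothing in the study would ever pick up an event in transfer.* That goes too far. The physicians treating the infant are study staff, and the reporting sentence in the Data Safety and Monitoring Plan has no scan limit. What is lacking is systematic recording.
- *A reader might infer that the monitoring subsection and the Data Safety and Monitoring Plan contradict each other.* They can be read together: the PI may be meant to review exactly the events logged during the scan, and a prompt report can also follow institutional policy. That policy is not shown, so no contradiction is proven.
- *A reader might infer that the log undermines the minimal-risk opinion in the Risk/Benefit Analysis or the reassurance in the consent script.* Neither statement is said to rest on this log, so its window cannot conflict with them.
- *A reader might want a count of missed events.* Any such figure would need an event rate that the Protocol does not give.

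Sedation and contrast are declared outside the research and are no part of this point.

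**Conclusion.** The point holds as a cheap improvement. Followed exactly, the Protocol leaves events during the move, the transfers onto and off the custom table, and the return without an entry on its only described safety log. Such events are not barred from reaching the IRB, but they are not captured by any set process, and an empty log is evidence about the scanning interval alone.

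This rests on reading the scan window in line with the Protocol's own headings. The exposure figure of about 224 table transfers a year also assumes one exam per consent and accrual as under the predecessor protocol. The size of the under-count is unknown. Without a comparator, a wider log would still not show that risk is lower than with conventional MRI; it would only make the record match the use of the device.

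**What to change.** Make three changes to the text.

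1. In Monitoring of safety and tolerability, extend both the monitoring sentence and the recording sentence. The window should start with the move to the control room and the transfer onto the patient table, and end when the infant is off the table and back at the bedside. Include the staff who carry out these steps among those who watch for events.
2. On the existing log form, add the phase of each entry: transfer, scan or return.
3. In the Data Safety and Monitoring Plan, state that the adverse events the PI reviews are those recorded in this window.

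Leave the prompt full report to the IRB as it stands, and leave the reporting of unanticipated problems unrestricted. Loosening the former in favour of a policy that is not shown could weaken an explicit safety duty. The end of the window should be the return to the bedside, not an open period for later effects. Monitor switching at the bedside, vital signs and chart review need no change.

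The cost is a few sentences and one field on a form. The nurse or physician who performs the transfer is already there; an event noticed on the return must be passed back to the control-room log. There will be a little more logging, some background neonatal events will be recorded, and the count may no longer be zero. Because the prompt-report duty is kept, each added entry also brings a report.
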